#### 6.2.8. Period A: Day 42 (Phone Visit)

- Dosing compliance verification via phone to confirm reasons for missed/additional doses. **Based on blister card review and/or tablet count, any subject who is noted not to have taken at least 80% or has taken more than 120% of required doses at any scheduled visit during the study will be considered out of compliance and this must be recorded on the CRF and documented as a Medication Error on the CRF and the source documents.**
- Review and assess adverse events (AEs).
- Assessment of concomitant medications.
- Instruct subjects on continued daily dosing of PF-06649751 or placebo in accordance with randomized dose arm up-titration scheme (see [Table 2](#), Section 5.5.1, [Titration of PF-06649751](#)).

- Instruct subjects on continued adjunct stable L-Dopa (open-label) administration.

#### 6.2.9. Period A: Day 56 (Phone Visit)

- Dosing compliance verification via phone to confirm reasons for missed/additional doses. **Based on blister card review and/or tablet count, any subject who is noted not to have taken at least 80% or has taken more than 120% of required doses at any scheduled visit during the study will be considered out of compliance and this must be recorded on the CRF and documented as a Medication Error on the CRF and the source documents.**
- Review and assess adverse events (AEs).
- Assessment of concomitant medications.
- Instruct subjects on continued daily dosing of PF-06649751 or placebo in accordance with randomized dose arm up-titration scheme (see [Table 2](#), Section 5.5.1, [Titration of PF-06649751](#)).
- Instruct subjects on continued adjunct stable L-Dopa (open-label) administration.
- Review OFF time diary instructions including requirement to complete OFF time diary for 3 consecutive days during Week 10.

#### 6.2.10. Period A: Day 70 (Procedures may be used as screening for eligible and consenting subjects for the open label extension study)

- Dosing compliance verification (Investigational product accountability and documentation) while subject is present to confirm reasons for missed/additional doses. **Based on blister card review and/or tablet count, any subject who is noted not to have taken at least 80% or has taken more than 120% of required doses at any scheduled visit during the study will be considered out of compliance and this must be recorded on the CRF and documented as a Medication Error on the CRF and the source documents.**
- Collect and review OFF time diary while subject is present.
- Review and assess adverse events (AEs).
- Assessment of concomitant medications.
- Perform full physical and neurological examination.
- Collect weight.
- Collect blood and urine for safety lab tests.
- Collect Prolactin laboratory sample.

- Perform standard supine triplicate 12-lead electrocardiogram (ECG).
- Perform standard single supine and standing vitals (HR and blood pressure).
- Perform the Columbia Suicidality Severity Rating Scale (C-SSRS) “Since last evaluation”.
- PK blood sample collection for PF-06649751 concentration. The time of sample collection and the date and time of the most recent dose of study medication prior to PK sampling should be recorded in the source documentation.
- Perform MDS-UPDRS Parts I, II, III, and IV.
- CCI [REDACTED].
- Perform Questionnaire for Impulsive-Compulsive Disorders in Parkinson’s Disease – Rating Scale (QUIP-RS).
- CCI [REDACTED].
- Dispense Investigational Product.
- Dispense OFF time diary and review instructions including requirement to complete diary for 3 consecutive days during Week 15.
- Instruct subject on continued daily dosing of PF-06649751 or placebo in accordance with randomized dose arm up-titration scheme (see [Table 2](#), Section 5.5.1, [Titration of PF-06649751](#)).
- Instruct subjects on continued adjunct stable L-Dopa (open-label) administration.

- Instruct subject to begin simultaneous adjunct down-titration of stable L-Dopa dose (refer to Section 5.5.3, [Period B:](#) ).

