### 3.1.2. Double Blind Period

Eligible subjects will enter the 15 week double blind treatment phase, consisting of:

- Up to 3 week titration of PF-06649751 or placebo administered once daily to the randomized target dose ([Section 5.5.1](#)).
- 2 week stabilization period for dose adjustment after reaching the target dose with possible return to previous dose level after completion of the titration period. For subjects with intolerable adverse events, adjunct L-Dopa dose may subsequently be reduced after consultation with the Medical Monitor (see Section 5.5.1 [Titration of PF-06649751](#)).
- Period A (Primary Efficacy): a 5 week period of PF-06649751 or placebo administered once daily adjunctive to stable doses of L-Dopa ([Section 5.5.2](#)).
- Period B (Maintenance): a 5 week maintenance period of PF-06649751 or placebo administered once daily adjunctive to stable doses of L-Dopa ([Section 5.5.3](#)).

Subjects will return to the clinic at the end of Weeks 1, 2, 3, 4, 5, 10, 15, and 17. Weeks 2 and 3 may be conducted as phone visits, at the discretion of the investigator.

All other visits will be conducted as phone visits; as per Section 6.5 ([Unplanned Visits](#)), the investigator has the discretion to conduct an unplanned clinic visit if warranted for subject safety. For guidance on concomitant medications for Parkinson's disease and other disorders please see Section 5.8, [Concomitant Treatment\(s\)](#).

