**Table 2. Proposed Titration Schemes for PF-06649751 and Placebo Doses**

Week/ Start Day of Dose Level	Treatment Group				
	Placebo	1 mg	3 mg	7 mg	15 mg
Week 1 / from Day 1	P	1 mg	1 mg	1 mg	1 mg
Week 2/ from Day 8	P	1 mg	3 mg	3 mg	3 mg
Week 3 / from Day 15	P	1 mg	3 mg	7 mg	7 mg
Weeks 4-15 / from Day 22	P	1 mg	3 mg	7 mg	15 mg

**Titration (Week 1 to Week 3):** No modifications to the upward titration of Study Medication can be made. Subjects who experience intolerable adverse events during titration will need to be discontinued from the study.

**Post Week 3 (Week 4 to Week 5):** For subjects who experience unacceptable new adverse events after having achieved the target dose (after Day 21) and deemed related to the dose increase, the dose of investigational product can be changed to the previous dose level (Week 3 dose level). This results in a dose reduction from 15 mg/day to 7 mg/day for the highest dose group, and no change in dose for the other dose groups in a blinded fashion. Only one dose modification of investigational product is permitted.

**L-Dopa Adjustment for Unacceptable Dopaminergic Side Effects (Week 1 to Week 15):** In the case of unacceptable dopaminergic side effects and following discussion with the Medical Monitor, the dose of L-Dopa may be reduced between Day 1 and Day 105 visit.

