### 5.5.3. Period B: Maintenance

After the Week 10 Visit (primary endpoint collection), subjects will enter Period B. During Period B, double-blind treatment with investigational product will continue as adjunctive treatment to a stable dose of open label L-Dopa.

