### **5.8.3. Permitted Concomitant Medications**

Subjects will use background L-Dopa (for example, Sinemet, Menesit, Madopar, Prolopa, or EC Dopar) provided in the local commercial packaging throughout the study. Subjects should remain on the same formulation of L-Dopa from Screening through the duration of the study. The daily L-dopa dose should not change from 21 days prior to Day 0 (Randomization) through the end of the study. In the case of unacceptable dopaminergic side

effects, and only following discussion with the Medical Monitor, the dose of L-Dopa may be reduced between the Day 1 and Day 105 visit.

Stable doses of concomitant medications for treatment of medical conditions are permitted during the course of the study, including antihypertensives, antidepressants (other than MAO inhibitors), anticoagulants, lipid lowering agents, oral antidiabetics, thyroid replacement hormones, and antacids.

The potential risk for drug-drug-interactions with PF-06649751 and primary substrates of CYP3A4 (especially those with a narrow therapeutic index; eg, vinca alkaloids), and BCRP is considered to be low, but cannot be excluded as it has not been fully evaluated at this time. Therefore, caution is recommended when PF-06649751 is combined with BCRP (eg, rosuvastatin, methotrexate, mitoxantrone, etc.) or CYP3A substrates (eg, alfentanil, ergotamine, irinotecan, ticagrelor, simvastatin, etc.). Further information on potential drug-drug-interactions and data available to date can be found in Section 5.2.7 Pharmacokinetic-Drug Interactions of the Investigator's Brochure.

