## 6.2. Study Period

For the study period described below, there is a +3 day visit window for scheduling of visits during Weeks 1, 2, and 3.

For Weeks 4-19, the visit window for scheduling visits will be  $\pm 3$  days.

**Study visit times are relative to Day 0 (Randomization), and not relative to when the previous visit actually occurred. The indicated visit windows are only intended to mitigate scheduling conflicts for study visits, and efforts should be made to return the subject to the correct timelines.**

For each visit, the following chronology of events should be adhered to, where possible:

- Patient Reported Outcome scales (ie, [CCI](#), [QUIP-RS](#), [CCI](#)): obtain prior to UPDRS.
- UPDRS Assessment: obtain prior to ECGs.
- ECGs: obtain prior to blood pressure and heart rate.
- Blood pressure/pulse rate: obtain prior to safety laboratory tests.

- Safety laboratory tests: obtain prior to pharmacokinetic (PK) blood.
- Pharmacokinetic blood specimens.
- Other procedures may be obtained before or after those listed above.

### 6.2.1. Randomization: Day 0

- Assessment of prior/concomitant medications.
- Review changes in medical history since screening visit.
- Review Inclusion and Exclusion criteria.
- Perform brief physical and neurological examination.
- Collect blood and urine for safety lab tests. Screening labs must have no clinically significant findings, as judged by the investigator, in order for the subject to be dosed with PF-06649751 or placebo.
- Urine drug screening in the form of a dipstick performed at the site.
- CCI [REDACTED]
- Collect Prolactin laboratory sample.
- Perform standard supine triplicate 12-lead electrocardiogram (ECG).
- Perform standard single supine and standing vitals (HR and blood pressure) and assess subject temperature to confirm no symptoms of fever.
- Perform the Columbia Suicidality Severity Rating Scale (C-SSRS) “Since last evaluation”.
- Collect and review OFF time diary while subject is present; confirm subject eligibility for OFF time has been met.
- Perform MDS-UPDRS I, II, III, and IV.
- CCI [REDACTED]
- CCI [REDACTED]
- CCI [REDACTED]

- CCI [REDACTED].
- CCI [REDACTED].
- Perform Questionnaire for Impulsive-Compulsive Disorders in Parkinson's Disease – Rating Scale (QUIP-RS).
- Perform Oral Symbol Digit Modality Test (SDMT).
- Perform Modified Clinical Global Impression - Severity (MCGI-S).
- CCI [REDACTED].
- Review and assess adverse events (AEs).

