- Register subject as Randomized in IWR system in order to obtain randomization number.
- Dispense Investigational Product. Subjects will begin PF-06649751 or placebo dosing the following morning (Day 1).
- Instruct subjects on continued daily dosing of PF-06649751 or placebo in accordance with randomized dose arm up-titration scheme (see [Table 2](#), Section 5.5.1, [Titration of PF-06649751](#)) and instruct subjects on proper dosing documentation.
- Instruct subjects on continued adjunct stable L-Dopa (open-label) administration.

#### 6.2.2. Dosing: Day 1 through Day 105

- Continued once daily dosing of PF-06649751 or placebo in accordance with randomized dose arm up-titration scheme (see [Table 2](#), Section 5.5.1, [Titration of PF-06649751](#)).
- Continued adjunct stable open-label L-Dopa administration (through Period B).

#### 6.2.3. Titration Period: Day 7

- Dosing compliance verification (Investigational product accountability and documentation) while subject is present to confirm reasons for missed/additional doses. **Based on blister card review and/or tablet count, any subject who is noted not to have taken at least 80% or has taken more than 120% of required doses at any scheduled visit during the study will be considered out of compliance and this must be recorded on the CRF and documented as a Medication Error on the CRF and the source documents.**
- Review and assess adverse events (AEs).
- Assessment of concomitant medications.

- Perform the Columbia Suicidality Severity Rating Scale (C-SSRS) “Since last evaluation”.
- Perform standard supine triplicate 12-lead electrocardiogram (ECG).
- Perform standard single supine and standing vitals (HR and blood pressure).
- Perform MDS-UPDRS Part III.
- Dispense OFF time diary, review instructions including requirement to wait until the next phone visit before completion of the diary.
- Dispense Investigational Product. Next immediate dose level of PF-06649751 or placebo will be taken the next morning.
- Instruct subjects on continued daily dosing of PF-06649751 or placebo in accordance with randomized dose arm up-titration scheme (see [Table 2](#), Section 5.5.1, [Titration of PF-06649751](#)).
- Instruct subjects on continued adjunct stable L-Dopa (open-label) administration.

#### 6.2.4. Titration Period: Day 14

In the case of a phone visit:

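### The Day 70 procedures still tell sites to down-titrate L-Dopa, although every other description of Period B in the current protocol requires a stable dose

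*Protocol*

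**What the plan says.** The last two L-Dopa bullets for the Day 70 visit (Protocol Section 6.2.10) point in opposite directions. The first reads "Instruct subjects on continued adjunct stable L-Dopa (open-label) administration". The next reads "Instruct subject to begin simultaneous adjunct down-titration of stable L-Dopa dose" and cites Section 5.5.3 for the details.

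Section 5.5.3 gives no such details. It states: "During Period B, double-blind treatment with investigational product will continue as adjunctive treatment to a stable dose of open label L-Dopa". Section 5.8.3 is equally plain: "The daily L-dopa dose should not change from 21 days prior to Day 0 (Randomization) through the end of the study".

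The protocol allows two departures from a stable dose. Sections 5.5.1 and 5.8.3 permit a reduction for unacceptable dopaminergic effects once the Medical Monitor has been consulted; in the words of 5.5.1, "the dose of L-Dopa may be reduced between Day 1 and Day 105 visit". Section 5.9 permits rescue L-Dopa.

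SAP Section 2.2 repeats that Period B is on stable L-Dopa. It adds that a recommended downward titration in Period B belonged to the protocol before Amendment 2.

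**The concern.** The visit procedures are the text a site works from on the day. Here they direct an unconditional change to a patient's background Parkinson's treatment, and the cited section contains no scheme for making it. A site cannot comply with both bullets.

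**Patient care.** The bullet applies to every arm, placebo included, in a population selected for at least 2.5 hours of OFF time each day. A site following it would have to invent the size and pace of the reduction. The document history shows that Amendment 2 also removed the Week 11, 12 and 14 clinic visits and turned Week 13 into a phone visit. The instruction therefore survived while scheduled clinic contact in Period B was cut back.

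**Data.** The secondary efficacy endpoints cover the whole double-blind period. SAP Section 6 takes Week 15 data into models and summaries for subjects who consented under Amendment 2 before entering Period B. That rule sorts subjects by consent version, not by the L-Dopa dose they actually took. If some sites followed the bullet and others followed Section 5.5.3, Week 15 would combine stable and reduced L-Dopa. If all followed it, Week 15 would describe a regimen other than the one the plan states.

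**Working it through.** **1. Instructions side by side (current text, not the amendment log)**

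| Place | L-Dopa in Period B |
|---|---|
| Protocol 6.2.10, last bullet | Begin down-titration; see 5.5.3 |
| Protocol 6.2.10, preceding bullet | Keep stable |
| Protocol 5.5.3 | Stable; no reduction scheme |
| Protocol Summary (Study Design), 3.1, 3.1.2 | Five weeks on stable L-Dopa |
| Protocol 5.8.3 | Daily dose unchanged to end of study |
| Protocol 6.2.2 | Stable through Period B |
| Protocol 6.2.11 (Day 91 call) | Keep stable |
| SAP 2.2 | Stable; down-titration was pre-Amendment 2 |

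One bullet stands against all the rest. The exceptions do not rescue it. The side-effect reduction needs a clinical trigger and a discussion with the Medical Monitor, and rescue is L-Dopa given as needed. Neither is a planned reduction at Day 70.

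**2. Interval without a scheduled clinic visit**

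Inputs: clinic visits from Section 3.1.2 ("Subjects will return to the clinic at the end of Weeks 1, 2, 3, 4, 5, 10, 15, and 17"), so Week 10 (Day 70) is followed by Week 15 (Day 105); the Day 91 phone visit from Section 6.2.11; and the window from Section 6.2 ("For Weeks 4-19, the visit window for scheduling visits will be" ±3 days).

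- Plan's own figure: Period B lasts 5 weeks, and 5 × 7 = 35 days. Visit days give 105 − 70 = 35. Reproduced.
- Shortest clinic gap: (105 − 3) − (70 + 3) = 102 − 73 = 29 days.
- Longest clinic gap: (105 + 3) − (70 − 3) = 108 − 67 = 41 days.
- Day 70 to the phone call: 91 − 70 = 21 days; shortest (91 − 3) − (70 + 3) = 15; longest (91 + 3) − (70 − 3) = 27.

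**3. Which data are exposed**

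- Week 10 primary endpoint: SAP Section 3.1, rule 8, uses only diary days before the clinic visit. They precede the instruction, so there is no direct effect. Any influence would be indirect, because Week 15 values of eligible subjects enter the same repeated-measures model (SAP 5.2.2.1).
- Week 15 diary and MDS-UPDRS endpoints: analysed at all visits (SAP 6.2.1, 6.2.2), so exposed.
- Rescue after a reduction: SAP 3.1, rule 7, replaces OFF time on a rescue diary day with the baseline value, and in Period B this covers subjects who consented under Amendment 2 before entering it. Extra rescue use would therefore also alter Week 15 OFF time.

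**The case against.** The best reply is that this is an editing remnant and that the surrounding text corrects it. The bullet sends the reader to a section that says stable dose, the line above says stable dose, and the Day 91 call repeats it. A site would have to set aside several statements to act on one. This is fair: the design itself is not in doubt, and the fault is an internal inconsistency rather than a questionable design decision. But a site may rely on the visit checklist alone, and a wrong dosing instruction there should not depend on cross-checking to be caught.

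Second, the 35-day gap is the ordinary Period B schedule and would be the same without the bullet. That is correct. It measures how long a reduction could run before a scheduled clinic review, not the harm done. The Day 91 call reviews adverse events and medications, unplanned visits are allowed (Sections 3.1.2, 6.5), and rescue L-Dopa is available after a phone consultation (Section 5.9).

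Third, the efficacy decision criteria rest on Week 10, so the damage to the data is limited to Period B secondary results and depends on sites following the bullet. This also stands.

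Fourth, the SAP would not be blind to L-Dopa changes. Section 6.5.4 plans medication tables and listings, and summaries of Parkinson's medication use and rescue doses by treatment group; Section 4.2 plans a deviation review. That is so, although the one count of background medication changes excludes L-Dopa, and no visible summary counts L-Dopa dose changes by arm.

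Finally, parts of the amendment log are redacted, so what sites were told about the change to Period B cannot be seen. That limits any inference that sites were misled. It does not make the bullet correct.

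**Conclusion.** The concern holds. The last Day 70 bullet is wrong as written and should be corrected because it is a dosing instruction. The exposed interval is 35 days to the next scheduled clinic visit (29 to 41), with one phone contact at 21 days (15 to 27). These figures assume visits on schedule within the stated windows and no unplanned visit.

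The consequences for patients and for Week 15 data are conditional on a site acting on the bullet. The documents give no evidence that one did, and no enrolment dates relative to Amendment 2, so neither the number of subjects nor an effect at Week 15 can be estimated. The Week 10 primary analysis is not directly affected.

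**What to change.** Delete the down-titration bullet from Section 6.2.10. Tell sites in writing that L-Dopa stays at its stable dose through Day 105, except for side-effect reductions discussed with the Medical Monitor (Sections 5.5.1 and 5.8.3) and rescue use (Section 5.9).

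The cost is one deleted line plus a clarification letter or administrative amendment. Sample size, analysis methods and visit schedule do not change, and the SAP needs no revision. If subjects have already passed Day 70 under this text, their recorded L-Dopa doses and dates, which Section 5.8 already requires, will show whether anyone acted on it.

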#### 6.2.11. Period B: Day 91 (Phone Visit)

- Dosing compliance verification via phone to confirm reasons for missed/additional doses. **Based on blister card review and/or tablet count, any subject who is noted not to have taken at least 80% or has taken more than 120% of required doses at any scheduled visit during the study will be considered out of compliance and this must be recorded on the CRF and documented as a Medication Error on the CRF and the source documents.**
- Review and assess adverse events (AEs).
- Assessment of concomitant medications.
- Instruct subject on continued daily dosing of PF-06649751 or placebo in accordance with randomized dose arm up-titration scheme (see [Table 2](#), Section 5.5.1, [Titration of PF-06649751](#)).
- Instruct subjects on continued adjunct stable L-Dopa (open-label) administration.
- Review OFF time diary instructions including requirement to complete diary for 3 consecutive days during Week 15.

#### 6.2.12. Period B: Day 105 (Procedures may be used as Visit 1 for eligible and consenting subjects for the open label extension study)

- Dosing compliance verification (Investigational product accountability and documentation) while subject is present to confirm reasons for missed/additional doses. **Based on blister card review and/or tablet count, any subject who is noted not to have taken at least 80% or has taken more than 120% of required doses at any scheduled visit during the study will be considered out of compliance and this must be recorded on the CRF and documented as a Medication Error on the CRF and the source documents.**
- Collect and review OFF time diary while subject is present.
- Review and assess adverse events (AEs).
- Assessment of concomitant medications.
- Perform full physical and neurological examination.
- Collect blood and urine for safety lab tests.
- Collect Prolactin laboratory sample.

- Perform standard supine triplicate 12-lead electrocardiogram (ECG).
- Perform standard single supine and standing vitals (HR and blood pressure).
- Perform the Columbia Suicidality Severity Rating Scale (C-SSRS) “Since last evaluation”.
- PK blood sample collection for PF-06649751 concentration. The time of sample collection and the date and time of the most recent dose of study medication prior to PK sampling should be recorded in the source documentation.
- Perform MDS-UPDRS Parts I, II, III, and IV.
- CCI [REDACTED]
- Perform Questionnaire for Impulsive-Compulsive Disorders in Parkinson’s Disease – Rating Scale (QUIP-RS).
- CCI [REDACTED]
- Perform Physician Withdrawal Checklist (PWC-20).

